### **9.3.2. Analysis of Secondary Endpoints**

#### **9.3.2.1. Overall Survival**

OS is defined as the time from date of randomization to date of death due to any cause. Patients last known to be alive will be censored at date of last contact.

OS will be hierarchically tested for significance at the time of PFS analyses, provided the primary endpoint, PFS, is statistically significant at the PFS interim or final analyses. In addition, OS will be tested at 69% and 88% of the OS events and at the OS final analysis. A

stratified log-rank test (1-sided) stratified by randomization stratification factors will be used at the interim and/or final analyses with the overall significance level preserved at 0.025 (1-sided). OS time associated with each treatment arm will be summarized using the Kaplan-Meier method and displayed graphically where appropriate. CIs for the 25th, 50th, and 75th percentiles will be reported. The Cox proportional hazards model will be fitted to compute the treatment hazard ratio and the corresponding 95% CI.

#### **9.3.2.2. Pathologic Complete Response**

Pathologic complete response is defined as the absence of histologically identifiable residual cancer in any resected specimen. The pathological complete response rate on each treatment arm will be estimated by dividing the number of patients with pathological complete response recorded from randomization until PD per modified RECIST v1.1 or death due to any cause by the number of patients randomized to the respective treatment arm. The corresponding exact 2-sided 95% CIs will be provided by treatment arm.

#### **9.3.2.3. Objective Response**

Objective response (OR) is defined as a CR or PR per RECIST v1.1 ([Appendix 4](#)) recorded from randomization until disease progression per modified RECIST v1.1 ([Appendix 3](#)) or death due to any cause. A patient will be considered to have achieved an OR if the patient has a CR or PR which does not need to be confirmed at a subsequent assessment. Additionally, patients with inadequate data for tumor assessment (eg, no baseline assessment or no follow-up assessments) will be considered as non-responders in the ORR analysis.

The ORR on each treatment arm will be estimated by dividing the number of patients with OR (CR or PR) by the number of patients randomized to the respective treatment arm. The corresponding exact 2-sided 95% CIs will be provided by treatment arm. The CR rate and PR rate analyses will be performed similarly. In addition, the best overall response for each patient will be summarized by treatment arm.

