#### **3.4. Surgical Salvage of Residual Disease after Completion of the CRT Phase**

[figure not shown]
Treatment of residual disease at the primary site will be determined by the investigator and the clinical situation (see [Figure 4](#)). If treatment at the primary site is necessary after completion of CRT, study treatment has failed and the patient will discontinue the study treatment. Surgical resection, re-irradiation, chemotherapy, or palliative care may be performed per institutional policy. If the primary site is cleared of residual disease yet residual disease at the cervical nodal basin is suggested by imaging/clinical evaluation, then selective neck dissection will be performed unless a cytologic sampling of the node is negative. Residual disease in the neck is not considered a treatment failure if surgical salvage is completed within 140 days of completion of CRT. A primary treatment neck dissection after completion of the CRT Phase will be defined as a neck dissection performed for residual disease and within 20 weeks (140 days) of completion of CRT. Patients who undergo such a primary treatment neck dissection will not be considered experiencing a disease progression event and remain on study treatment, regardless whether neck specimens are positive or negative.

Positive specimens removed within 140 days of completion of CRT will be considered part of the initial treatment plan and not considered failures of initial management; positive specimens upon neck dissection beyond 140 days will be considered regional failures. Such consolidation neck dissections after completion of the CRT Phase will encompass only the areas (typically only levels 2 and 3) initially involved in the side of the neck in question. The extent of neck dissections performed for nodal recurrence or nodal progression, and/or salvage of disease at the primary will be determined by the treating surgeon.

If a neck dissection is required, then the treating surgeon is required to contact the surgical Principal Investigator (PI) of this study, [name] prior to the surgery to discuss the clinical and radiologic findings as well as the planned surgery itself. Notes from the surgery, as well as the pathology report from the neck dissection, must also be submitted to [name] for review when they become available, but no later than 6 weeks following the procedure.

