**Table 2. Chemoradiation and Avelumab/Placebo Treatment Schedule**

	Lead-in Phase (7 days) a	CRT Phase (63 days)								Maintenance Phase b
	-- Day --	----- Day -----								
	1	1	8	15	22	25	29	36	39	43
IMRT (70 Gy/35 fractions/7 weeks; 1 fraction per day, 5 fractions/week [Monday – Friday])		X→	X→	X→	X	→	X→	X→	→	X→
Cisplatin (100 mg/m^2 Q3W)		X			X					X
Avelumab (10 mg/kg) or placebo	X		X		X c			X		Q2W

- Lead-in Phase to start 7 days prior to initiation of CRT Phase.
- Maintenance Phase to start after completion of the CRT Phase (ie, 2 weeks following completion of CRT) and be 12 months in duration. CRT phase may be extended as required for patient recovery from CRT; however, it is hypothesized that patients will receive maximal benefit from beginning maintenance as close to the scheduled time as possible.
- Day 25 dose of avelumab/placebo during the CRT Phase may be administered between Day 24 and Day 29. Cisplatin should be administered on a Monday or Tuesday if feasible to maximize overlap with IMRT. CRT = Chemoradiotherapy; IMRT = intensity-modulated radiation therapy; Q2W = every 2 weeks; Q3W = every 3 weeks.

The investigator will assess antitumor activity based on radiological assessments and clinical evaluation of patients using modified RECIST v1.1 at baseline, 12 weeks after the completion of CRT (ie, 10 weeks following completion of the CRT Phase of the study), every 16 weeks thereafter for 48 months (208 weeks), and every 24 weeks thereafter until confirmed disease progression per modified RECIST v1.1 and regardless of discontinuation of study treatment or initiation of subsequent anti-cancer therapy.

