### 6.2.2.8. Objective response

**Best overall response (BOR)** will be assessed based on reported overall lesion responses at different evaluation time points from the date of randomization until the first documentation of PD, according to the following rules.

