#### **BOR Based on Unconfirmed Responses**

- uCR = one CR documented before first documentation of PD
- uPR = one PR documented before first documentation of PD (and not qualifying for a CR)
- SD (applicable only to patients with measurable disease at baseline) = at least one SD assessment (or better)  $\geq 6$  weeks after date of randomization and before first documentation of PD (and not qualifying for uCR or uPR).
- Non-uCR/Non-PD (applicable only to patients with non-measurable disease at baseline) = at least one non-uCR/non-PD assessment (or better)  $\geq 6$  weeks after date of randomization and before first documentation of PD (and not qualifying for uCR or uPR).
- PD = PD after date of randomization (and not qualifying for uCR, uPR or SD).
- NE: all other cases.

An objective status of uPR or SD cannot follow one of uCR. SD can follow uPR only in the rare case that tumor increases by less than 20% from the nadir, but enough that a previously documented 30% decrease from baseline no longer holds.

**Unconfirmed Objective Response (uOR)** is defined as BOR of uCR or uPR. A patient will be considered to have achieved a uOR if the patient has a uCR or uPR which does not need to be confirmed at a subsequent assessment.

Patients who do not have a post-baseline radiographic tumor assessment or clinical evaluation due to early progression, who die, progress, or drop out for any reason prior to reaching a uCR or uPR will be counted as non-responders in the assessment of uOR. Each patient will have an objective response status (0: no uOR; 1: uOR). uOR rate (uORR) is the proportion of patients with uOR in the analysis set.

uORR by treatment arm will be calculated along with the 2-sided 95% CI using the Clopper-Pearson method (exact CI for a binomial proportion as computed by default by the FREQ procedure using the EXACT option).

In addition, the frequency (number and percentage) of patients with uBOR of uCR, uPR, SD, non-uCR/non-PD (applicable only to patients with non-measurable disease at baseline), PD and NE will be tabulated. Patients with uBOR of NE will be summarized by reason for having NE status. The following reasons will be used:

- No baseline assessment
- No post-baseline assessments due to death

- No post-baseline assessments due to other reasons
- All post-baseline assessments have overall response NE
- SD of insufficient duration (<6 weeks after date of randomization)

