#### Period for Derivation of BOR and PFS

The period is defined from randomization until PD per RECIST v1.1 (Appendix 4 of B9991016 protocol) or death due to any cause.

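### Objective response has no analysis that stops at new anti-cancer therapy, so a CR or PR first seen on non-study systemic therapy started before PD is credited to the assigned arm

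*Protocol*

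**What the plan says.** Protocol 9.3.2.3 defines objective response as a CR or PR "recorded from randomization until disease progression per modified RECIST v1.1" or death, with no confirmation needed. SAP 3.2.2 repeats this. SAP 6.2.2.8 derives best overall response from assessments "at different evaluation time points from the date of randomization until the first documentation of PD", and its rule for complete response reads "uCR = one CR documented before first documentation of PD". The rule for partial response is parallel. For the separate standard-RECIST derivation, SAP Appendix 3 states: "The period is defined from randomization until PD per RECIST v1.1", or death.

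The SAP 6.2.2.8 non-responder rule covers patients "who die, progress, or drop out for any reason prior to reaching a uCR or uPR will be counted as non-responders". It does not mention a change of therapy.

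Tumor assessments continue "regardless of discontinuation of study treatment or initiation of subsequent anti-cancer therapy" (SAP 2.2; likewise Protocol 7.8). Protocol 3.1 provides for patients who start new therapy before PD and keeps them on the scan schedule. Protocol 5.8.3 bars other systemic anti-cancer therapy during the CRT and Maintenance Phases but prohibits nothing in post-treatment follow-up.

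SAP 5.2.6 defines a start date for new anti-cancer therapy. SAP 5.3.3.4 says that this date serves sensitivity efficacy censoring and the end of the on-treatment period. The analyses that use it for efficacy are the PFS analyses M1, S1 and M1_B in SAP 6.2.2.2.

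**The concern.** Objective response serves the stated objective of anti-tumor activity of the assigned regimen. A response that first appears on another drug is not evidence of that activity, yet the present rules count it. Protocol 3.4 says "If treatment at the primary site is necessary after completion of CRT, study treatment has failed", and it lists chemotherapy among the options. If that disease is not biopsied, or the biopsy is not positive, no PD is recorded and the same patient can later be an objective responder.

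Miscredited responses would raise the ORR and carry into DR and TTR. A patient already in PR who reaches CR on the new drug would also move into the CR rate. If the share of such patients differs by arm, the odds ratio and the CMH test at 1-sided nominal 0.025 (SAP 6.2.2.8) are biased, in a direction the documents do not fix. The plan has no output that would show whether this happened.

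**Working it through.** Neither document gives an expected ORR, an effect size for response, or a rate of new therapy before PD. There is no planned figure to reproduce, so the check is mainly textual.

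**1. Does any rule close the window at new therapy?** No. Protocol 9.3.2.3 and SAP 3.2.2, 6.2.2.8 and Appendix 3 all close it at PD or death only. Drop-out in the non-responder rule does not fill the gap, because a patient who changes therapy and stays on the scan schedule has not dropped out.

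**2. Would such a response be seen?** Yes. Scans continue after new therapy. The first scheduled response scan is 10 weeks after the CRT Phase (SAP 2.2). On the planned schedule that is 7 + 63 + 70 = 140 days after Lead-in Day 1. This is a separate quantity from the 140-day neck-dissection window, which runs from completion of CRT. A patient who changes therapy earlier has all scheduled response scans on or after the new drug.

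**3. Which routes are already closed?**

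| Situation | Rule | Result |
|---|---|---|
| Target lesion excised or re-irradiated off study | Protocol Appendix 4; SAP Appendix 3 | Indeterminate / not evaluable, no CR or PR |
| Salvage of primary, tumor on pathology | Protocol 3.3 | PD |
| Unresolved primary at 12 weeks, biopsy positive | Protocol 7.1 | PD |
| Distant progression | Protocol 3.3 | PD, pathology not mandatory |
| Other systemic therapy during CRT or Maintenance | Protocol 5.8.3 | Prohibited |
| Growth meeting standard RECIST PD, no biopsy | SAP 6.2.2 and Appendix 3 | Closes the standard-RECIST window only |

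**4. What stays open?** A patient off study treatment, with residual or unbiopsied locoregional disease and no confirmed PD, who starts systemic therapy without a prior response. Under modified RECIST this includes radiographic growth without pathology. Under standard RECIST it is mainly residual disease that has not met RECIST progression. Protocol 7.1 expects that some biopsies will not be done, and SAP 6.2.2.2 tabulates those not performed or inconclusive. Locally treated non-target lesions are also outside the excised/irradiated rule.

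**5. Size.** About 640 patients randomized 1:1 gives about 320 per arm.

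- One miscredited response moves an arm's ORR by 1/320 = 0.0031, or 0.31 percentage points.
- If shares eA and eB of the arms are miscredited, observed difference = true difference + eA − eB. With eA = eB the difference is unchanged, though both ORRs are inflated.

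Illustration only; every input is assumed: control ORR 60% to 80%, true difference +8 points, 320 per arm, unstratified 1-sided test at 0.025.

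| eA, eB | Extra responders (A, B) | Observed difference | Power |
|---|---|---|---|
| 0, 0 | 0, 0 | 8 points | 0.56 to 0.79 |
| 1%, 1% | 3.2, 3.2 | 8 + 1 − 1 = 8 points | 0.56 to 0.81 |
| 1%, 3% | 3.2, 9.6 | 8 + 1 − 3 = 6 points | 0.36 to 0.59 |
| 2%, 5% | 6.4, 16.0 | 8 + 2 − 5 = 5 points | 0.27 to 0.48 |

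For scale, the 95% half-width of the ORR difference is about 1.96 × √(2p(1−p)/320): 7.6 points at p = 0.60 and 6.2 points at p = 0.80. A handful of miscredited responses is small against that.

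**The case against.** The strongest reply is that the open window is a consistent treatment-policy choice. Primary PFS counts events whatever therapy intervenes (Protocol 9.3.1, SAP 6.1.1.1), time to locoregional failure and time to distant metastasis do the same (SAP 6.2.2.4, 6.2.2.5), and DR takes its censoring from PFS (Protocol 9.3.2.4). Redefining response alone would break that alignment. This stands against replacing the definition. It does not stand against adding an analysis: the treatment-policy rule is written out for those endpoints but not for response, and PFS has a stopped-at-new-therapy counterpart while response has none.

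It is also fair that the route is narrow, that the standard-RECIST response analysis closes much of it for growing disease, and that response is secondary, tested at nominal alpha outside the PFS/OS hierarchy.

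Three stronger readings are tempting and not supported:

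- A reader might infer that responses to salvage treatment in general are credited. For surgery and re-irradiation of target lesions the evaluability rule blocks this, and salvage of the primary with tumor on pathology is itself PD.
- A reader might size the problem by multiplying the 15% to 36% response rates in Protocol 1.3 by a guessed share of switchers. Those rates are for recurrent disease. Response here is measured against the pre-CRT baseline, so a patient already 30% below it is a responder before any new drug, and a patient with growing disease must fall 30% below the pre-CRT sum. The share of switchers is not in the documents.
- A reader might scale the arms by the planning hazard ratio of 0.68 and conclude bias toward no difference. That ratio concerns PFS events, and these patients by definition have had none.

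**Conclusion.** The gap holds in narrow form. A CR or PR first documented after non-study systemic therapy, started before PD, counts for the assigned arm, and no planned response analysis shows how many there are. The only exact figure is 0.31 percentage points of ORR per such response, given about 320 patients per arm. The total, and the direction of any bias in the comparison, depend on rates of new therapy before PD that the documents do not give; equal rates leave the ORR difference unchanged. A reader might infer that the endpoint must be redefined or that the trial's main result is at risk. Neither follows, because PFS and OS do not use this window. This is a cheap improvement to a secondary endpoint.

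**What to change.** In SAP 6.2.2.8 and Appendix 3, add a prespecified analysis of BOR and uOR in which only assessments up to the earliest of PD, death or the SAP 5.2.6 new-therapy date count. Carry the same responders and cut-off into DR and TTR, with DR censored at the last adequate assessment before new therapy, as M1 does for PFS. Report it beside the present definition, and say in 6.2.2.8 that the present definition is a treatment-policy one.

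Two exemptions are needed, because the SAP 5.2.6 date includes resections and curative-intent radiation:

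- Neck dissection within 140 days of completing CRT, which Protocol 3.3 treats as part of initial treatment.
- Off-protocol completion of the assigned CRT, which Protocol 1.2.2 reports has occurred.

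State that other resections recorded under SAP 5.2.6 do close the window, so that the programming is unambiguous.

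The cost is a short paragraph and minor programming on a date the SAP already derives and imputes. The downside is that patients who start new therapy before their first post-baseline scan become non-responders in this analysis, so its ORR may be slightly lower.

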#### **9.3.2.4. Duration of Response**

Duration of response (DR) is defined, for patients with an objective response, as the time from the first documentation of objective tumor response (CR or PR) to the first documentation of PD per modified RECIST v1.1 or death due to any cause, whichever occurs first. Censoring rules for DR will follow those described above for PFS. DR will be summarized by treatment arm using Kaplan-Meier method and displayed graphically, where appropriate. The median DR and 95% CI for the median will be provided for each treatment arm.

#### **9.3.2.5. Locoregional Failure**

Locoregional failure (LRF) is defined as the time from the date of randomization to the date of the first documentation of locoregional recurrence or death due to any cause, whichever occurs first. LRF will be summarized by treatment arm using Kaplan-Meier method and displayed graphically, where appropriate. The median LRF and 95% CI for the median will be provided for each treatment arm.

### **9.3.2.6. Distant Metastatic Failure**

Distant metastatic failure or distant metastasis (DM) is defined as the time from the date of randomization to the date of the first documentation of distant metastatic or death due to any cause, whichever occurs first. DM will be summarized by treatment arm using Kaplan-Meier method and displayed graphically, where appropriate. The median DM and 95% CI for the median will be provided for each treatment arm.

### **9.3.2.7. Neck Dissection**

The rate of neck dissection on each treatment arm will be estimated by dividing the number of patients with neck dissection recorded from randomization until PD per modified RECIST v1.1 or death due to any cause by the number of patients randomized to the respective treatment arm. The corresponding exact 2-sided 95% CIs will be provided by treatment arm.

The rate of pathologically-positive neck dissection and rate of pathologically-negative neck dissection will be analyzed in the same way as the rate of neck dissection.

